3.2 Randomization

Subjects will be randomly assigned to one of the two treatment groups by the Clinical Monitor as they are recruited using a rolling recruitment method. Cohort assignment will be made by serially selecting from a list of 44 randomly generated three-digit subject identification numbers, with 22 subjects in each Active and Control group, respectively.

3.3 Primary Endpoint and Observational Measures

The primary outcome measure is the Composite SOT score. Observational measures are the Neurobehavioral Symptom Inventory, California Verbal Learning Test, Brief Symptom Inventory, Wechsler Adult Intelligence Scale – Symbol Search and Coding, Pittsburgh Sleep Quality Index, Headache Disability Index, Physiologic Stress Response, Quantitative Gait Assessment using EMG, 6-minute walk test, Dynamic Gait Index, and Computerized Video Nystagmography. The observational measures will provide essential data for potential future studies investigating CN-NINM effects on a particular functional deficit.

4.0 STUDY OUTCOMES

4.1 Primary Outcome

NeuroCom CDP Sensory Organization Test (SOT) - Measures standing dynamic balance.

4.2 Secondary Outcomes

- 6-Minute Walk Test - over ground (6MWT) - Measures walking speed.
- Dynamic Gait Index (DGI) – assesses walking, walking with head turns, over and around obstacles, and stairs.
- Physiological Stress Test: resting & post exercise, heart rate, respiration, skin conductance, core temperature.
- Neurobehavioral Symptom Inventory (NSI) - Subjective inventory of TBI symptoms.
- California Verbal Learning Test (CVLT) – Assesses short- and long-term verbal memory.
- Brief Symptom Inventory 18 (BSI 18) – Assesses anxiety symptoms.
- Wechsler Adult Intelligence Scale – Symbol Search and Coding (WAIS-IV) – Assesses visual spatial abilities.
- Pittsburgh Sleep Quality Index (PSQI) - Subjective inventory of sleep habits, duration and quality.
- Headache Disability Index (HDI) – Assesses frequency & severity of headaches
- Quantitative Gait Assessment and EMG – to measure stride length and width, and muscle activation patterns during gait.
- Computerized video nystagmography (VNG) - Measures eye movement control.

4.3 Primary Efficacy Endpoints

The primary efficacy endpoint is the change in the SOT score from Baseline to the Week 2 and Week 14 visits. That is, if X_1 is the endpoint then:

$$X_1 = \text{Composite SOT score at Week 2 visit} - \text{Composite SOT score at Baseline.}$$

Similarly, X_2 is:

$$X_2 = \text{Composite SOT score at Week 14 visit} - \text{Composite SOT score at Baseline.}$$

4.4 Secondary Efficacy Endpoints

As stated above, there are multiple secondary efficacy endpoints.

4.5 Safety Endpoints

The primary safety endpoint is the frequency of falls, measured in daily activity logs. The secondary safety endpoint is the frequency of headaches as assessed by Headache Disability Index.

AEs and unanticipated (unexpected) AEs will be assessed and recorded.

5.0 PLANNED ANALYSIS

The following planned analyses will be performed by the unmasked study statistician, who will be communicating with the Data Safety Monitoring Committee (DSMC).

5.1 Interim Analysis

Only one interim analysis is planned after first 22 subjects have completed their Week 14 visit. The interim analysis will be performed using the primary efficacy endpoint for the data of first 22 subjects that have completed the Week 2 and Week 14 visits. The two treatment groups will be listed as Group 1 and Group 2 to maintain the blinding of the treatments.

The number of subjects (most likely 11), and both the Mean and standard deviation (SD) for each group will be calculated by the study statistician. Student's *t*-test will be used to compare the two means. A *p*-value will be generated but no decision will be made at the interim analysis time, and the trial will continue to completion unless there are serious safety concerns.

The study statistician will present the interim analysis results (*n*, Mean and SD) by treatment group in unblinded fashion including the *p*-value to the DSMC.

Also, the statistician will present these results to the sponsor of the study but in the blinded fashion, by identifying the treatment groups only as Group 1 and Group 2.

5.2 Final Analysis

The study statistician will perform the final analysis using the primary efficacy endpoints when all 44 subjects have completed their Week 26 visit. Just like at interim analysis, mean and SD of each group will be calculated. Student's *t*-test will be used to compare the two groups and *p*-value will be reported.

Secondary analyses will consider group differences on measurements at a visit as well as change from baseline.

Descriptive statistics will be calculated for outcome and demographic variables. Mean and SD will be used for numeric variables and count (percent) will be used for categorical variables. The percentage of subjects compliant in each group will be calculated. Statistical comparisons between the groups will be made using Student's t-test for numeric data and chi-squared procedures for categorical data.

Data for comparison between the treatments are collected at baseline, week 2, week 5, week 8, week 11, week 14, week 17, week 20, week 23, and week 26 visits. Each subject has up to 10 data points collected for each of the outcome variables. Data at the end of each Stage (week 2, week 14, week 26) will be used for statistical comparison between the treatment groups. Statistical comparison between groups will be based on Student's t-test.

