- University of Wisconsin – Madison Health Sciences Human Subjects IRB.
- University of Wisconsin – Institute for Clinical and Translational Research – Data Monitoring Committee.

Coded data (results only) will be shared with the MRMC via secure email for purposes of informing future studies.

Statistical Considerations

Sample Size Estimation

This study will be an experimental investigation and will employ descriptive statistics to discover the mean changes from baseline for Control and Active, and then calculate true effect sizes and corresponding variances both within and between the two treatment groups. It is a first step in an iterative, incremental process to generate enough data to make reasonable power calculations in subsequent controlled studies. We believe this approach is justified because we have a very small data set from which to draw estimates of effect size, and none regarding a control group response. Our estimates are based on large changes in SOT scores in the previous pilot study involving 4 civilian subjects with mild to moderate concussive TBI using an Active device.

For this study we have assumed that the Control group response will be half that of the active group. Using a two-sample *t*-test to estimate the sample sizes of the experimental group and the control group, and assuming equal variances in the two treatment groups with $\sigma = 0.5$; a 2-tailed significance level, $\alpha = 0.05$; the true difference of the means = 0.5, and setting the power at 0.80, we calculate that a cohort of 17 subjects in each arm is sufficient. Based on our previous experience in two controlled pilot studies, we estimate a drop-out rate of not more than 25%. In using this conservative estimate, we believe the study is sufficiently powered at 22 subjects per treatment group (44 subjects total) to generate the data necessary to calculate effect sizes and cohorts in the future.

Primary Endpoints and Observational Measures

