The primary outcome measure is the Composite SOT score. Observational measures are the Neurobehavioral Symptom Inventory, California Verbal Learning Test, Brief Symptom Inventory, Wechsler Adult Intelligence Scale – Symbol Search and Coding, Pittsburgh Sleep Quality Index, Headache Disability Index, Physiologic Stress Response, Quantitative Gait Assessment using EMG, 6 minute walk test, Dynamic Gait Index, and Computerized Video Nystagmography. The observational measures will provide essential data for potential future studies investigating CN-NINM effects on a particular functional deficit.

Data Analysis

An interim analysis will be performed when 22 subjects have completed the second phase (At-Home Training), and a full investigation at the completion of the study.

- **Interim Analysis:** In compliance with the request from the funding agency (US Army Medical Research and Materiel Command), a single independent interim analysis will be conducted under a Statistical Analysis Plan (SAP) developed for this study and reviewed by the Biostatistics Group at ICTR. The primary independent measure: Active vs. Control PoNS. The interim analysis will be performed after 22 subjects have completed the 6th data point (at 14 weeks - the completion of the At-Home phase of the study)

The primary analysis will be conducted under the intention-to-treat principal, and all data will be included. We will not conduct a missing data imputation analysis. Every attempt will be made to obtain follow-up data on subjects who withdraw from treatment.

The interim analysis will be performed using the primary efficacy endpoint for the data of first 22 subjects that have completed the Week 2 and Week 14 visits. The two treatment groups will be listed only as "Group 1" and "Group 2" to maintain the blinding of the treatments.

The number of subjects (most likely 11), and both the Mean and standard deviation (SD) for each group will be calculated by the study statistician. Student's *t*-test will be used to compare the two means. A *p*-value will be generated but no decision will be made at the interim analysis time, and the trial will continue to completion unless there are serious safety concerns.

The study statistician will present the interim analysis results (*n*, Mean, and SD) by treatment group in unblinded fashion including the *p*-value to the DSMC.

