Also, the statistician will present these results to the sponsor of the study but in the blinded fashion by identifying the treatment groups only as Group 1 and Group 2.

- **Final Analysis:** A repeated-measures ANOVA will be performed on the data derived from the 10 outcome measures gathered for each subject. Both individual (*n*=1) and cohort data set (*n*=22) analysis will be conducted to identify both specific and generalizable effects of the intervention methods. Sub-analysis by gender and age in both treatment groups will also be performed to assess the relative response of females and males.

Evidence of efficacy will be determined by significant differences in outcome measures both within and between groups after both the two-week intensive phase and at conclusion of the 14 weeks. Changes of 8 points in the SOT are considered clinically significant.

Data logs for each individual will be entered into the OnCore Data Management System used by ICTR for independent analysis and experimental verification.

Risks/Benefits Assessment

Potential Risks

1. **Electrotactile Stimulation.** The sensation could become uncomfortable at high intensity levels, which could be distressing to the subject. Some subjects have reported a mild tingling sensation that lasts from several minutes up to an hour after the stimulus is turned off. Although this sensation may feel unusual, it is not reported to be annoying and does not interfere with normal activities.

2. Excess Salivation. Subjects may experience excess salivation due to the presence of the PoNS in the mouth.
3. Disease Transmission. Because more than one subject may use the same device, there is a potential for disease transmission.
4. Falls. Subjects will be performing balance and gait tasks that may cause them to lose their balance or fall.
5. Decreased Performance or No Improvement in Symptoms. There is a risk that when subjects stop using the device, they will not retain any improvements they may have gained while doing CN-NINM training and their function will return to its prior level. There is also the possibility that CN-NINM training will not improve their symptoms.
6. Confidentiality. There is a risk that someone who is not involved in performing or monitoring this study could view study information.

Minimizing Risk

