3.0 STATISTICAL CONSIDERATIONS

3.1 Sample Size Calculations

This study is an investigation to discover changes in the Composite SOT scores of subjects from baseline at the end of Week 2 and Week 14 visits in Active and Control groups.

The sample size for the study is based on the primary endpoint of change in mean SOT score from baseline at the end of Week 2 and Week 14 visits. The following assumptions are made:

- Control group response is half of that of the Active group
- Two-sided Test
- Equal variances in both groups
- Alpha Level= 0.05
- Power = 80%
- μ_{A1} = Mean change in SOT score from baseline to the end of Week 2 visit in Active group
- μ_{A2} = Mean change in SOT score from baseline to the end of Week 14 visit in Active group.
- μ_{C1} = Mean change in SOT score from baseline to the end of Week 2 visit in Control group
- μ_{C2} = Mean change in SOT score from baseline to the end of Week 14 visit in Control group.

To calculate the sample size, the following two hypotheses, Null (H_0) and Alternative (H_A) are formulated:

$$H_0: \mu_A = 2\mu_C \quad \text{VS.} \quad H_A: \mu_A \neq 2\mu_C$$

Since there is very limited experience on PoNS™ device and no data on control device, to calculate a sample size for this study, the mean change of 26.3 in composite SOT score at the end of Week 2 visit from baseline from the pilot study is used. Also it is assumed that the Control group response will be half of that of the Active group and equal variability in both groups with common standard deviation of 13.2, a 50% coefficient of variation in the Active group.

Based on the above assumptions, a sample size of 17 subjects in each group will have 80% power to detect a difference between the Treatment PoNS™ group mean μ_A , of 26.3 and the Control group mean μ_C , of 13.2 assuming that the common standard deviation is 13.2 using a two group t-test with a 0.05 two-sided significance level.

Previous experience in two controlled pilot studies, a drop-out rate of not more than 25% is estimated. Therefore, using conservative approach, the sample size for this study is increased from 34 to 44 subjects with 22 subjects in each arm.

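### The protocol's final analysis is a 10-visit repeated-measures ANOVA with no deciding term, the SAP's is Student's t-tests at Weeks 2 and 14, and no text says which governs

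*SAP*

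**What the plan says.** **Protocol, Data Analysis, Final Analysis:** "A repeated-measures ANOVA will be performed on the data derived from the 10 outcome measures gathered for each subject". The Study Design section shows that these 10 are time points on the SOT and gait measures. No factor, interaction or contrast is named as the deciding test. The efficacy rule follows: "Evidence of efficacy will be determined by significant differences in outcome measures both within and between groups after both the two-week intensive phase", and again at the end of the 14 weeks.

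**SAP 4.3 and 5.2:** "The primary efficacy endpoint is the change in the SOT score from Baseline to the Week 2 and Week 14 visits". Section 5.2 applies Student's t-test to these endpoints. It lists all 10 visits, then limits group comparisons to the ends of the stages (Weeks 2, 14 and 26): "Statistical comparison between groups will be based on Student's t-test". It contains no ANOVA and no within-group test.

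**Link between the documents:** the protocol mentions the SAP only under Interim Analysis: "a single independent interim analysis will be conducted under a Statistical Analysis Plan (SAP) developed for this study". For that look both documents use Student's t-test.

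**Sizing:** both documents use a two-sample t-test. The SAP (3.1) sizes "using a two group t-test with a 0.05 two-sided significance level". The protocol states "we calculate that a cohort of 17 subjects in each arm is sufficient".

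**The concern.** Two different final analyses of the same primary outcome stand in current text, so two final results would be available. They ask different questions. A 10-visit ANOVA includes baseline and four withdrawal-stage visits, while the t-tests ask about benefit after 2 and 14 weeks. They may also use different subjects. Under the protocol's complete-case rule, a classical repeated-measures ANOVA loses anyone who misses one of 10 visits, whereas a t-test needs only baseline and the visit tested.

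Timing adds to this. SAP 5.0 says "The following planned analyses will be performed by the unmasked study statistician", and that statistician will already have compared the groups at the interim look. A choice between methods is most credible if it is written down before then.

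**Working it through.** **1. The plan's own figure.** Inputs from SAP 3.1: mean changes 26.3 and 13.2 (difference 13.1), common SD 13.2, two-sided alpha 0.05. Power comes from the noncentral t distribution with noncentrality 13.1 / (13.2 × sqrt(1/n1 + 1/n2)).
- 17 + 17: 13.1 / (13.2 × 0.343) = 2.89, df 32, power 0.801. At 16 per arm it is 0.775, so 17 is reproduced.
- The protocol's inputs (difference 0.5, SD 0.5) give 0.807 at 17 per arm.
- At the 25% dropout ceiling, 44 × 0.25 = 11 are lost and 33 remain. With 17 + 16, SE = 13.2 × sqrt(1/17 + 1/16) = 4.60, df 31, power 0.788.

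**2. How far the two plans diverge.** This needs assumptions that the documents do not supply. I assumed:
- 17 + 16 subjects, all with 10 visits;
- SD of change to Week 14 equal to 13.2;
- correlation 0.5 or 0.7 between baseline and Week 14, either constant across visits or decaying with time;
- a difference of 13.1 from Week 2 to Week 14, with 0, 50 or 100% of it kept after withdrawal.

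The table gives the share of simulated trials in which the two tests fall on opposite sides of 0.05.

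| Comparison | Disagreement |
|---|---|
| Week 14 t-test vs ANOVA Week 14 contrast | about 5-10% |
| Week 14 t-test vs omnibus group-by-visit test | about 20-39% |
| Week 14 t-test vs ANOVA group main effect | about 27-66% |
| Benchmark: Week 2 t-test vs Week 14 t-test | about 21-26% |

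The main effect diverges most because it averages over baseline and the withdrawal visits. With 17 per arm and constant correlation, its power ran from 24% to 92% as the correlation and the persistence of benefit varied. Each single-visit t-test stayed near 80%.

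**3. The two-visit rule.** With no true effect, at least one of the two t-tests is significant in 9.2-9.7% of simulated trials. At the planned effect, both are significant in 66-80%. The documents do not plainly say which rule applies.

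**4. Baseline SOT as a covariate.** Baseline is recorded at screening (Protocol, Subject Screening Procedure) and must precede randomisation (SAP 8.1). Let b be the slope of follow-up on baseline and f the share of baseline variance left by the entry cut-off. Relative to the change score, ANCOVA multiplies the error variance by (1 + b) / ((1 + b) + (1 - b)f). For example, b = 0.5 and f = 1 give 1.5/2.0 = 0.75. Both b and f are assumed. Power with 17 + 16, df 30:

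| b | 0.3 | 0.5 | 0.7 | 0.8 |
|---|---|---|---|---|
| f = 1 | 0.928 | 0.889 | 0.849 | 0.828 |
| f = 0.2 | 0.827 | 0.813 | 0.801 | 0.796 |
| f = 0.2, chance baseline imbalance simulated | 0.813 | 0.799 | 0.787 | 0.782 |

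The comparator is 0.788 for the t-test.

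**The case against.** The strongest reply is that the SAP plainly governs. Its t-test sized the trial in both documents, is attached to the primary endpoints, and is used in both documents for the interim look, which SAP 5.2 says the final analysis follows. The protocol never calls its ANOVA primary, and it describes the study as informing later ones. Much of this stands: the evidence favours the t-test as the intended analysis, and the fix should adopt it. It does not settle the matter. No sentence gives the SAP precedence for the final analysis, SAP 1.1 sets an objective of demonstrating superior efficacy, and the protocol's efficacy rule rests on significance.

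A reader might infer three stronger things.
- *The t-test is wrong or underpowered.* It is valid and reaches its stated power at 17 per arm. ANCOVA appears in neither document and is an efficiency choice.
- *The conflict would probably reverse the trial's result.* The high disagreement figures depend on which ANOVA term is read in and on assumed correlations. A Week 14 contrast seldom disagrees, and the SAP's two t-tests disagree with each other about as often as the lower omnibus figures.
- *The choice would be made on unblinded results.* The documents show that the opportunity exists, not that anyone intends it.

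**Conclusion.** The conflict is real and should be resolved before the interim analysis. It is one of precedence and specification, and it does not rest on any simulation. Its practical size runs from about 5-10% to 27-66% disagreement, depending on the unnamed ANOVA term and on the assumptions in step 2.

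The within-group half of the protocol's efficacy rule also needs reconciling. The SAP has no matching test, and both documents assume that Control subjects improve by half the Active response (13.2 points in SAP 3.1). On the plan's own assumptions, within-group improvement therefore does not separate the devices.

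Baseline adjustment is worthwhile but not required. Power would be 0.93-0.83 for assumed slopes of 0.3-0.8. There would be little or no gain, or a trivial loss (0.782 against 0.788), if the entry cut-off leaves about 20% of baseline variance.

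**What to change.** **Must be done, in both documents, before the interim analysis:**
- Name the between-group comparison of change in composite SOT at Weeks 2 and 14 as the primary final analysis, and label the protocol's 10-visit ANOVA as supportive.
- Say whether efficacy requires a between-group difference at both visits, or name one visit as primary.
- State that within-group differences are descriptive and not evidence of efficacy.

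**Improvement, not error correction:** fit the primary comparison as ANCOVA with group and baseline SOT, and keep the unadjusted Student's t-test as a sensitivity analysis.

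**Minor and separate:** carry the protocol's complete-case rule into the SAP, and define the sensitivity analysis that the protocol promises, using the SOT visits already scheduled. SAP 5.2 times the final analysis at completion of Week 26 by all 44 subjects, although dropout of up to 25% without replacement is expected. It should instead wait until every randomised subject has completed Week 26 or withdrawn.

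**Cost:** a few sentences for the required part and one model term for the improvement. The missing-data sensitivity analysis adds some programming. No new data, visits or subjects are needed.

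### The SAP fixes the pooled-variance Student's t-test for its numeric between-arm comparisons; naming Welch's test instead would guard against unequal SDs combined with uneven dropout, at almost no cost.

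*SAP*

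**What the plan says.** For the final analysis, SAP 5.2 compares the primary endpoint by Student's t-test. It extends the test to other numeric variables ("Statistical comparisons between the groups will be made using Student's t-test for numeric data and chi-squared procedures for categorical data") and says of the end-of-stage data at weeks 2, 14 and 26 that "Statistical comparison between groups will be based on Student's t-test". SAP 5.1 uses the same test at the interim look. The SAP names no unequal-variance version and plans no check of the variances.

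Equal variance enters as a sample-size assumption in SAP 3.1: "Equal variances in both groups". The only SD in SOT points is described there as a "common standard deviation of 13.2, a 50% coefficient of variation in the Active group", and the same section says that no data exist on the control device. The Protocol (Sample Size Estimation) also assumes equal variances, on a standardised scale.

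Both documents allow for dropout of up to 25% and give no split by arm. The Protocol (Missing Data) does not replace dropouts. It plans a complete-case analysis and a sensitivity analysis for missing outcomes.

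The Protocol's final analysis (Data Analysis) is a different method: "A repeated-measures ANOVA will be performed on the data derived from the 10 outcome measures gathered for each subject".

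**The concern.** Student's test pools the two sample variances. When the true variances differ, the pooled standard error is right on average only if the arms are equal in size. If the more variable arm is the smaller, the standard error is too small and false positives exceed 5%. If it is the larger, the standard error is too big and power is lost.

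Nothing in the documents rules out either condition. The common SD was carried over to Control without data, and the number of completers per arm is left to chance. A plausible route to unequal SDs is a treatment that helps some subjects and not others, which could widen the spread in one arm without moving the means far apart. At stake are the nominal level of the primary comparison and, in the opposite configuration, some power.

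**Working it through.** **Inputs from the documents.** SAP 3.1: mean change 26.3 (Active) and 13.2 (Control), common SD 13.2, "Two-sided Test", "Alpha Level= 0.05", 80% power, 17 per arm raised to 22, dropout up to 25%.

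**Assumptions not in the documents.** SD ratio between arms: range 1.25 to 3. Split of dropout: the main case loses about a quarter of one arm and none of the other. Since 22 × 0.75 = 16.5, this gives 16 or 17 v 22.

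**Step 1: the plan's own figure.** The difference is 26.3 − 13.2 = 13.1. The noncentrality is (13.1/13.2) × √(17/2) = 2.89 on 32 degrees of freedom. Power is 80.1% at 17 per arm and 77.5% at 16, so the stated 17 reproduces.

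**Step 2: what the SD assumption implies.** 50% of 26.3 is 13.15, rounded to 13.2. Giving Control the same SD implies a coefficient of variation of 13.2/13.2 = 100% there. If Control instead had a 50% coefficient at its planned mean, its SD would be 6.6, a ratio of 2. That ratio arises only when the means differ. At equal means a constant coefficient gives equal SDs. Step 4 therefore treats the ratio as a free assumption and does not derive it from the 50% figure.

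**Step 3: mechanism, with SDs 13.2 and 6.6** (variances 174.24 and 43.56). The expected pooled variance is [(n₁−1)σ₁² + (n₂−1)σ₂²]/(n₁+n₂−2). The pooled SE is the root of that times (1/n₁+1/n₂). The true SE is √(σ₁²/n₁ + σ₂²/n₂).

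- 16 (more variable) v 22: pooled variance (15 × 174.24 + 21 × 43.56)/36 = 98.01, pooled SE 3.25, true SE √(10.89 + 1.98) = 3.59. The pooled SE is too small.
- 22 (more variable) v 16: pooled variance (21 × 174.24 + 15 × 43.56)/36 = 119.79, pooled SE 3.60, true SE √(7.92 + 2.72) = 3.26. The pooled SE is too large.
- 22 v 22: both are 3.15.

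**Step 4: size of the tests.** Sample variances were drawn as scaled chi-square (400,000 draws per case) and the normal tail of the mean difference was taken exactly. The null is equal mean change, which is what a two-sample t-test tests. The first-named arm is the more variable.

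| Completers | SD ratio 1.25 | 1.5 | 2 | 3 |
|---|---|---|---|---|
| 22 v 22 | 5.0% | 5.1% | 5.2% | 5.4% |
| 17 v 17 | 5.0% | 5.1% | 5.3% | 5.5% |
| 17 v 22 | 5.7% | 6.3% | 7.2% | 8.3% |
| 16 v 22 | 5.9% | 6.6% | 7.8% | 9.1% |
| 22 v 16 | 4.3% | 3.8–3.9% | 3.4% | 3.0% |

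The table shows Student's test; Welch's test gave 4.9–5.1% in every case. If all 11 dropouts (25% of 44) came from one arm, 11 v 22 at a ratio of 2 would give 11.4% or 1.9%. With 25% random dropout in each arm at a ratio of 2, averaged over the resulting arm sizes, Student's size is 5.4%.

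**Step 5: power.** With equal SDs and 17 per arm, Student has 80.1% and Welch 80.0%. With SD ratio 2, 22 v 16 (larger arm more variable) and a true difference of 8 points, the change that the Protocol calls clinically significant, Student has 59% and Welch 66%. In the reverse configuration, 17 v 22 with a difference of 13.1, Student rejects more often (96.6% v 94.7%), but there its size is also above 5%.

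**The case against.** The strongest objection is that the plan shows no reason for the SDs to differ when the treatment has no effect. Both documents assume equal variances. A reader might infer from the 50% coefficient of variation that Control has half the SD and that the type I error is therefore inflated. That inference fails, because the twofold ratio disappears once the means are equal. This part of the objection stands in full.

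The second objection is that a headline range of roughly 3–8% stacks two assumptions. It needs a twofold SD ratio as well as the loss of about a quarter of one arm with none from the other. The 25% is an overall ceiling with no split, and balanced random dropout leaves the size near 5.4%. The Protocol also undertakes to seek follow-up data on subjects who stop treatment. This stands too: the range is conditional and does not estimate this trial's error rate.

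Three other strong readings are not supported:

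- Not every between-arm test is affected. Categorical data use chi-squared procedures, and the Protocol's final analysis is a repeated-measures ANOVA.
- No interim consequence is shown. SAP 5.1 says "A *p*-value will be generated but no decision will be made at the interim analysis time" and expects about 11 per arm. At 11 v 11 with a ratio of 2, Student's size is 5.4%.
- Wrong confidence intervals cannot be charged to the plan, because neither document specifies one for the between-arm difference.

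The objection does not remove the exposure. The equal-variance assumption is untested, the numbers of completers may diverge, and the alternative test costs almost nothing.

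**Conclusion.** The point holds as a minor, optional improvement. With equal completers, Student's test is adequate: 5.0–5.5% for SD ratios up to 3 at 17 or 22 per arm. It departs materially from 5% only if SDs differ despite equal mean changes and dropout also falls mainly on one arm. The documents neither state nor exclude either condition. At 16 v 22 completers the departure is to about 6.6% or 3.8–3.9% at an SD ratio of 1.5, and to about 7.8% or 3.4% at a ratio of 2. The direction depends on which arm is smaller. Welch's test removes the dependence on both assumptions. The sample size is unaffected.

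**What to change.** In SAP 5.2, and in 5.1 for consistency, replace Student's t-test with Welch's unequal-variance t-test for numeric between-arm comparisons. Keep the equal-SD assumption in SAP 3.1 for the sample-size calculation only.

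The SAP's t-test and the Protocol's repeated-measures ANOVA have to be reconciled in any case. If the repeated-measures analysis is retained, allow arm-specific variances or use robust standard errors.

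The change is a phrase in each section, with no effect on conduct or enrolment. If the variances are truly equal, it costs about 0.1 percentage point of power at 17 per arm. Specifying the test in advance also avoids choosing one after the group SDs have been seen, since SAP 5.1 shows them to the sponsor by coded group at the interim.
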